2. OBJECTIVES

Objective:

Primary objectives

Evaluation of the implementation of a continuous monitoring method on the surgical ward

- Fidelity: The usability and degree of implementation of the Healthdot at the surgical ward
- Acceptability: The workload regarding the amount of spot checks in addition to the standard monitoring.

Secondary objectives

- Adoption: The intention and attitude towards the use of the Healthdot monitoring method.
- Feasibility: The extent to which the Healthdot monitoring method can be successfully carried out by the healthcare employees
- Acceptability: The workload regarding the amount of spot checks per hospital admission day per patient
- Acceptability: The perception among nursing staff given the satisfactory and agreeableness regarding workload.
- Appropriateness: Relation between device false alarms (noise) and correct alarms based on the alarming protocol.
- Appropriateness: Number of unexpected events that occur during or result from the use of the Healthdot medical device.
- Feasibility: The amount of time needed to perform and process a complete manual spot check or digital monitoring check.
- Costs: Cost-effectiveness analysis based on the duration of admission, the associated admission costs and the monitoring method
- Advanced algorithm analyses for improved monitoring protocols

Primary hypothesis:

Previous own research (TRICA-trial, PEACH-trial) (15, 17) has shown that the Healthdot monitoring device is non-inferior to manual monitoring with EWS on the surgical ward regarding predicting and alarming of deteriorating patients based on vital parameter alterations. Our hypothesis is that implementation of this new monitoring method is a challenge but that a stepwise and careful approach, with involvement of all healthcare staff, will have a positive effect on the nursing workload and efficiency without reduction in

confidence and thereby improvement of the overall workability and efficiency at the surgical ward.

Secondary hypothesis:

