6. INVESTIGATIONAL PRODUCT

a. Name and description of investigational product(s)

The Healthdot is a CE marked wearable data logger (15, 17). It consists of an adhesive layer, electronics and a battery. The intern mechanism contains an accelerometer which is able to measure movement including movement of the lung and heart. This movement data is processed with a validated algorithm to calculate heart rate, respiratory rate, posture and physical activity which are stored on the device and transferred through the LoRa network via the local gateway and/or gateways provided by KPN. The entire technological infrastructure system consists of:

- 1. Healthdot
- 2. Gateway
- 3. KPN-LoRa network
- 4. Server
- 5. Guardian dashboard

Required training

The investigators, nursing staff and physicians will receive a training and e-learning during the pre-implementation phase about the application of the Healthdot, the activation sequence and data reading. In addition, the structure of the study with the questionnaires, the timetable, the procedures in cases of malfunctions/ ADEs will be provided in a protocol.

Contra-indications

- Known to have severe allergy for the tissue adhesive used in the Healthdot.
- Any skin condition, for example prior severe rash, discoloration, scars or open wounds at the area of application
- Pregnant, or breastfeeding
- Use of topical that is known to influence the skin at the test area (such as medical and nonmedical creams or lotions)
- Patient with active implantables such as Implantable Cardioverter Defibrillator (ICD) and pacemaker

SWITCH - Surgical Ward Innovation: Telemonitored controlled by Healthdot

Evaluation of implementation

- Unable to understand instructions
- Left lower rib (place where Healthdot will be applied) is involved in the area of surgery, area of disinfection or area where bandages are needed.
- Transfer to a different ward during hospitalization

Indications for switching Healthdot

- No successful measurement after 4 hours or earlier if clinically necessary.
- When the Healthdot is not connected within 60 min after application

Indications to remove the Healthdot

• In case that an exclusion criterion is met during the study

b. Summary of findings from non-clinical studies

Research into the implementation of a new technology in healthcare can only be investigated in a clinical setting. No non-clinical studies are therefore contributing.

c. Summary of known and potential risks and benefits

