Additional anonymized data will, in case of informed consent, be collected from the electronic patient file such age, gender, reason for admission, medical history, duration of admission, complications and laboratory results. This additional data will be used to relate the primary and secondary results to any influencing factors/ baseline characteristics and potentially correct for these factors.

Variables eCRF

Characteristic	Input
Indication	Open
Type of invasive interventions/surgery	Open
Gender	M/F
Age	Open
BMI	Kg/m2
Comorbidities	
Charlson comorbidity index	Charlson Comorbidity Index (CCI) - MDCalc
Hospital stay	
Admission date	D/M/Y
Discharge date	D/M/Y
Elective or emergency	Open
Complications	
Clavien-Dindo classification	Grade I-V
Complications type	Cardiac, Pulmonary, Kidney failure,
	infectious, traumatic, surgical related
	(perforation, leakage, bleeding)
Urgent consultations (SIT) during	0-99
hospitalization	
ICU admission	Yes/no
Mortality <30 days	Yes/no
Re-admission < 30 days	Yes/no
Fidelity	
Total minutes monitored	Min
Amount of heart rate measurements	Total number per admission
Amount of respiratory rate measurements	Total number per admission
Artefact heart rate measurements	Total number per admission
Artefact respiratory rate measurements	Total number per admission
Total amount of spot checks	Total number per admission
Device	
Premature removal of device	Yes/no
Replacement of device	Yes/no
Bijzonderheden device	Yes/no

b. Randomisation, blinding and treatment allocation

N/A

c. Project procedures

Prior to the start of the pre-implementation phase there will be a pre-implementation phase during months 1-2. This phase will consist of training the medical staff through e-learning and physical meetings. During this phase, medical staff will have the opportunity to apply the Healthdot, learn to activate it and practise with the Guardian dashboard. This phase serves as preparation for the implementation and aims to optimize the intra-structure in advance. In addition, during this phase, baseline data will be collected about the standard spot check measurements, feeling of confidence and attitude towards a change in the monitoring method. This study is a quality project and a change in standard of care. Nurses and physicians voluntarily participating in the focus group will sign informed consent for participation. Nurses not participating in the focus group but working at the surgical ward during this project will

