During the first phase, the daily output will consist of:

• 3x daily spot check according to the hospital protocol where the vital values are manually entered in the electronic patient file and scored with EWS. In addition, the Healthdot will be applied for training purposes. Data from the Healthdot during this phase will not be used in clinical care.

Alarmsignalen bij vitaal bedreigde patiënt 2							
EWS Score	3	2	1	0	1	2	3
Hartfrequentie		<40	40-50	51-100	101-110	111-130	>130
Bloeddruk (syst)	<70	70-80	81-100	101-200		>200	
Ademfrequentie		<9		9-14	15-20	21-30	>30
Temperatuur		<35,1	35,1-36,5	36,6-37,5	>37,5		
Bewustzijn				Α	v	Р	U
A = Alert V = Reactie op aanspreken P = Reactie op pijn U = Geen reactie							
Wanneer u ongerust bent over de conditie van de patiënt: I punt extra							
Wanneer de urineproductie <75 ml gedurende de afgelopen 4 uur: I punt extra SIT:							
Indien de saturatie <	90 ondanks	therapie: ->	3 punten			sein 1	[name]

Table 2: Current (M)EWS protocol at the Catharina hospital for ward monitoring

During phase 2, the Healthdot is the primary monitoring method. Each patient admitted to the surgical ward will receive the Healthdot during intake until discharge. In case the hospitalization duration is longer than the battery life, approximately 14 days, the Healthdot will be replaced by a new device. The Healthdot measures heart rate, respiration rate and physical activity every 5 minutes. These parameters are displayed in the Guardian dashboard as a trendline and automatically transferred to the electronic patient file 3 times a day (08u,12u,17u). These measurements are scored in accordance with the alarm protocol and, if necessary, provide a notification. In case of an additional measurement, a spot check will be performed by the nursing staff.

The protocol alarms in case the respiration rate is above 20/min and or the heart rate is 110 or more for 15 minutes consecutive.

Score	0	+1	+2] [CREWS	
Vital parameter							
Heart rate	<110		≥110		0-1	2	3
Respiration rate	<20	≥20					

Table 3: New CREWS protocol for monitoring with Healhtdot on the ward

Indications for spot check monitoring

- Based on previous research, the Healthdot measurements can be relied upon, and no additional spot check monitoring will be routinely necessary for respiration and heart rate unless clinical doubt about the obtained value.

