- Additional spot check monitoring for blood pressure, oxygen saturation and temperature may be requested by any member of the treatment team

Premature termination of the study

• In the event that the International Workload Scale (IWS) (13) is in the highest category at moment 4-5 for more than 50% of the staff.

d. Withdrawal of individual subjects

Subjects of the core group can leave the study at any time for any reason if they wish to do so without any consequences.

i. Replacement of individual subjects after withdrawal

Participants who withdraw their participation from the core group won't be replaced.

e. Follow-up of subjects withdrawn from treatment

N/A

f. Premature termination of the study

In case the International Workload Scale (IWS) will be in the highest category of this scale for more than 50% of the staff at month 4-5 during phase two of this project.

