9. ADMINISTRATIVE ASPECTS, MONITORING AND PUBLICATION

a. Handling and storage of data and documents

Paper research documents are stored in a folder in a lockable cabinet at the primary investigators office.

Digital data will be collected with use of research manager. Access to this system will be logged and encrypted.

b. Monitoring and Quality Assurance

Monthly evaluation, starting after 3 months, with the focus group to assure the safety and quality of care during this project. Thereby, repetitive measurements of the IWS will provide important information regarding the safety of care and base of support from all involved.

c. Amendments

Amendments are changes made to the research after a favourable opinion by the accredited METC has been given. All amendments will be notified to the METC that gave a favourable opinion.

A 'substantial amendment' is defined as an amendment to the terms of the METC application, or to the protocol or any other supporting documentation, that is likely to affect to a significant degree:

- the safety or physical or mental integrity of the subjects of the trial;
- the scientific value of the trial;
- the conduct or management of the trial; or
- the quality or safety of any intervention used in the trial.

All substantial amendments will be notified to the METC and to the competent authority.

Non-substantial amendments will not be notified to the accredited METC and the competent authority, but will be recorded and filed by the sponsor.

d. Annual progress report

N/A for nWMO project

e. Annual safety report

N/A for nWMO project

f. Temporary halt and (prematurely) end of study report

N/A for nWMO project

g. Public disclosure and publication policy

The results will be processed into one or more scientific articles that will be submitted to scientific journals in the field of monitoring, surgery, medical technology and general health care. Publication rights belong to the investigator. Research results are the property of the sponsor.

SWITCH - Surgical Ward Innovation: Telemonitored controlled by Healthdot

Evaluation of implementation

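### The only termination rule and the only safety measure named for the monthly evaluation are the same staff-workload rating; patient events are collected but not directed to that evaluation

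*Combined protocol and SAP*

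**What the plan says.** Premature termination is described twice, in 7.c and in 7.f, with the same single trigger: "the International Workload Scale (IWS) will be in the highest category of this scale for more than 50% of the staff at month 4-5". (The scale is called Integrated elsewhere in the protocol; I take it to be the same instrument.)

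Section 9.b provides for "Monthly evaluation, starting after 3 months, with the focus group to assure the safety and quality of care during this project". It then adds that "repetitive measurements of the IWS will provide important information regarding the safety of care". It names no other measure.

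In phase 2 the Healthdot becomes the primary monitoring method. Section 7.c states that "no additional spot check monitoring will be routinely necessary for respiration and heart rate unless clinical doubt about the obtained value", and that the treatment team may ask for blood pressure, saturation and temperature. The primary hypothesis in section 2 is that the new method "will have a positive effect on the nursing workload and efficiency".

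The eCRF in 7.a.iii holds SIT calls, ICU admission, Clavien-Dindo grade and "Mortality <30 days". The stated purpose is that these data "will be used to relate the primary and secondary results to any influencing factors/ baseline characteristics", with possible adjustment for them. ADEs are a secondary endpoint, entered in Table 2 of section 3 at month 6. Section 6.a says that "the procedures in cases of malfunctions/ ADEs will be provided in a protocol"; that protocol is not among the documents.

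**The concern.** A safety signal should move when patients do worse. The IWS asks nurses how loaded they are. Phase 2 takes routine tasks away from them, so the rating can fall simply because checks were dropped. A reassuring IWS in months 4 and 5 could then be read as reassurance about patients when it carries little information about them.

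Phase 2 is also when routine manual checks are withdrawn, so a ward-level rise in deterioration would appear then. If the monthly evaluation looks only at what 9.b names, the events that could show such a rise may not be tabulated until all phase 2 patients have passed through the ward.

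**Working it through.** The point rests on the text. The only arithmetic is the number of patients concerned.

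**1. What the termination rule measures.** The IWS in section 11 has nine categories. The highest describes work that cannot be completed even with very great effort. The rule needs over half of staff to be there. That is a test of whether the ward can cope.

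**2. Which way phase 2 should move it.** Phase 1 has three manual checks a day. Phase 2 drops routine manual heart rate and respiration and makes the remaining vital signs on request. A 20% reduction in spot checks is a primary success criterion (7.a.i), and section 2 predicts better workload. All of these point to a lower IWS without reference to patient outcome. The link to patients is not nil: sicker patients mean more work, and the top category's description includes having too many problems. It is indirect and is offset by the tasks removed.

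**3. Where patient events go.**

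| Item | Where recorded | Stated use or timing |
|---|---|---|
| SIT calls | eCRF, 7.a.iii | relating results to influencing factors; possible adjustment |
| ICU admission | eCRF, 7.a.iii | same |
| Clavien-Dindo complications | eCRF, 7.a.iii | same |
| 30-day mortality | eCRF, 7.a.iii | same |
| ADEs | secondary endpoint, 7.a.ii | Table 2: month 6; Table 4: descriptive statistics |
| IWS | staff questionnaire | Table 2: months 0 to 6; named in 7.c, 7.f and 9.b |

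Only the last row is tied to the monthly evaluation or to a decision to stop.

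**4. How many patients.** Section 4 gives a turnover of 900-1000 a year and plans 250 patients per phase.

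- Upper turnover: 1000 / 12 × 3 = 250, which reproduces the plan's figure.
- Lower turnover: 900 / 12 × 3 = 225.
- Per month: 900 / 12 = 75 to 1000 / 12 ≈ 83.
- Still to be admitted after month 4: 2 × 75 = 150 to 2 × 83.3 ≈ 167.
- Still to be admitted after month 5: 75 to 83.

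Reviews after months 4 and 5 could therefore still affect care for up to about two thirds and one third of phase 2 admissions. These figures assume even inflow. They count admissions; eCRF data come only from consenting patients.

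**5. What cannot be computed.** The documents give no rate for ICU admission, death, complications or SIT calls. The chance of detecting a given rise, or of a false alarm, would rest wholly on assumed rates and an assumed action level. I give neither.

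**The case against.** The strongest reply is that this is a quality project outside the Dutch research act (nWMO), introducing a CE-marked device as the new standard of care. Formal patient-event stopping boundaries belong to interventional trials. The core group has about 10 nurses and 5 physicians from the ward, is to meet monthly with an explicit safety aim, and can raise an ICU transfer or a death without being told to. Individual patients keep device alarms, on-request checks and clinical observation, and device problems have their own protocol.

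Most of this stands. It disposes of several stronger readings that a reader might infer:

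- **That patient safety is not monitored.** Not supported: 9.b sets a safety evaluation and individual safeguards run throughout.
- **That device events have no handling rules.** Cannot be established: 6.a refers to a protocol that is not shown.
- **That month 6 is left unprotected because the rule covers months 4-5.** This has little force: the rule helps decide whether month 6 takes place, and the study period then ends.
- **That a numeric stopping level is needed.** The documents offer no event rate on which to base one.
- **That a periodic review of counts is the only remaining protection.** It is not: individual safeguards act sooner, and so would event-by-event review.

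What the reply does not answer is that 9.b assigns the safety role to a measure expected to improve when checks are removed. Individual safeguards do not show a ward-level rise. The group may raise events informally, but the plan does not ensure that it sees counts.

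**Conclusion.** The point holds in limited form. The sole study-level termination rule is a workload rule, and the sole measure 9.b names as information on safety of care is the same workload rating. Patient events are collected but not directed to the monthly evaluation.

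About 225-250 phase 2 admissions are concerned. The documents give no sign that harm is expected, and the size of any missed signal cannot be estimated from them. The conclusion assumes that the unseen malfunction/ADE protocol does not already send patient-event counts to the focus group; if it does, a cross-reference would largely settle the matter. I rate this as a worthwhile, inexpensive improvement and not a condition for running the project.

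**What to change.** 1. In 7.c and 7.f, label the IWS rule a workload or feasibility stop. In 9.b, state that a low IWS is not evidence of patient safety.
2. In 9.b, require the existing monthly evaluation after months 4 and 5 to review cumulative phase 2 counts of SIT calls, ICU admissions, Clavien-Dindo complications, deaths known to date and ADEs. Set them beside the months 1-3 figures, using the existing eCRF items and the ADE records already planned. Review any death or serious device event as it occurs. A concern leads to a review, not to automatic termination. Deaths known to date are specified because 30-day mortality is incomplete for recent admissions.
3. Make the same phase 1 versus phase 2 table, descriptive only, part of the decision after month 6 whether to extend.

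The cost is a short amendment and monthly rather than end-of-study entry of some fields. No new committee or eCRF item is needed. The limits should be stated: counts will be small, cover only consenting patients and can shift with case mix. Moderate rises may be missed, and some reviews will be due to chance. SIT calls need care, since a rise could reflect earlier recognition as well as more deterioration; read them together with ICU admissions and deaths.

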8. STATISTICAL ANALYSIS

The statistical analysis at professional (nurses/ physicians) level will be performed by means of descriptive statistics. Each continuous parameter is analyzed for normality by the Shapiro-Wilk test and visually by a figure. Normality-based reporting will be done using medians and interquartile ranges (IQR) or means and standard deviations (SD). Frequencies and percentages are reported for categorical data. Each continuous parameter is checked for normality by the Shapiro-Wilk test and visually by a figure. Normality-based reporting will be a figure. Normality-based reporting is performed using medians and interquartile ranges (IQR) or means and standard deviations (SD).

All analysis are performed using IBM SPSS Statistics 26.0 for Windows (IBM Armork, New York, USA) with 95% confidence interval and p < .05 as statistically significant.

The core group consisting of nurses, physicians and investigators will conduct a structured analysis into the fidelity, feasibility and acceptance of the implementation and this information is processed and objectified by means of a Braun and Clarke thematic analysis.

Objective	Instrument	Variable	Statistical test
Fidelity	SUS ^p	Continuous	Unpaired T-test/ Mann- Whitney U test
Acceptance	SC/day ^p SC/patient ^s IWS ^s	Continuous Continuous Ordinal	Descriptive statistics Descriptive statistics One-way ANOVA test
Adoption	EBPAS ^s	Continuous	Repeated measures ANOVA
Appropriateness	SNR ^s ADE ^s	Continuous Continuous	Descriptive statistics Descriptive statistics
Feasibility	Thematic analysis ^s	Nominal	Braun & Clarke thematic analysis
Time efficiency	Time measurement	Continuous	Descriptive statistics
Costs	Evaluation	Continuous	Descriptive statistics

Table 4: psychometric properties and statistical analysis

a. Other study parameters

N/A

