Previous research and findings from the literature show that the use of the Healthdot as a monitoring device is a validated measurement method that is at least as effective as the manually performed measurements with EWS according to the protocols in the Catharina hospital.

Serious adverse device events have not been established and mild adverse device events such as hypersensitivity reactions or rash have been observed only to a limited extent (15). Application of the Healthdot at the surgical ward is therefore possible in a safe manner, with the aim to implement this new monitoring method. Clinical observation and any additional spot checks remain available if indicated and the stepwise structure ensures optimization of the infrastructure before the implementation starts. This procedure optimally guarantees security and implementation can be carried out within a secure framework.

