7. METHODS

a. Study parameters/endpoints

i. Main study parameter/endpoint

Primary parameters and endpoints

Evaluation of the implementation of a continuous monitoring method on the surgical ward

- Fidelity: The usability and degree of implementation of the Healthdot at the surgical ward
 - Measured with the System usability scale (SUS), Score > 68 at M6 (8, 26)

- Acceptability: The workload regarding the amount of spot checks in addition to the standard monitoring.
 - Calculated with data from the electronic patient file records. Success in case of average reduction of 20% at M6 compared to M3

ii. Secondary study parameters/endpoints (if applicable)

Secondary parameter and endpoints

- Adoption: The intention and attitude towards the use of the Healthdot monitoring method.
 - Measured with evidence-based practise attitude scale (EBPAS) (9, 10).
- Feasibility: The extent to which the Healthdot monitoring method can be successfully carried out by the healthcare employees.
 - Measured with a thematic analysis (Braun and Clark) with core group (11).
- Acceptability: Amount of manual spot checks per hospital admission day per patient
 - \circ Calculated with data from the electronic patient file records.
- Acceptability: The perception among nursing staff given the satisfactory and agreeableness regarding workload.
 - Measured with the integrated workload scale (IWS) (12, 13).
- Appropriateness: Relation between device false alarms (noise) and correct alarms based on the alarming protocol.
 - Measured as signal to noise ratio (SNR)
- Appropriateness: Number of unexpected events that occur during or result from the use of the Healthdot medical device. Measured as adverse device events (ADE)
- Feasibility: The amount of time needed to perform and process a complete manual spot check or digital monitoring check. Measured manually.
- Costs: Cost-effectiveness analysis based on the duration of admission, the associated admission costs and the monitoring method
- Advanced algorithm analyses for improved monitoring protocols with advanced AI software

iii. Other study parameters (if applicable)

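### Table 4 classes adverse device events as continuous; summarised per patient, the section 8 rule would show median 0 (IQR 0-0) with up to about 24% of patients affected

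*Combined protocol and SAP*

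**What the plan says.** Section 7.a.ii defines the ADE endpoint as "Number of unexpected events that occur during or result from the use of the Healthdot medical device". It does not say whether this is counted per patient, per device or for the whole ward, and it gives no denominator. The measurement timetable in section 3 shows ADE once, at month 6, from administered data.

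The Appropriateness row of Table 4 (section 8) reads "SNR ^s ADE ^s Continuous Continuous Descriptive statistics Descriptive statistics". ADE and the alarm signal-to-noise ratio (SNR) therefore carry the same variable type and the same analysis.

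The text of section 8 says "Each continuous parameter is analyzed for normality by the Shapiro-Wilk test and visually by a figure". Continuous parameters are then reported as mean with SD or as median with IQR. For the other data type it says "Frequencies and percentages are reported for categorical data". The paragraph opens with "The statistical analysis at professional (nurses/ physicians) level will be performed by means of descriptive statistics", and no separate rule is given for patient-level or event-level data.

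On expected frequency, section 6.c says that "mild adverse device events such as hypersensitivity reactions or rash have been observed only to a limited extent". No rate is given.

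The eCRF table in section 7.a.iii has yes/no items for premature removal, replacement and device particularities, and an item for minutes monitored. It has no ADE item and no alarm counts.

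**The concern.** A number of adverse events is a count, and per patient it is close to a yes/no outcome. Calling it continuous sends it to the summary least able to describe it. When most patients have no event, the median and both quartiles are zero whether one patient or several dozen had a reaction.

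ADE is the only named device-safety endpoint. The early-termination rule in sections 7.c and 7.f uses workload alone, and section 9.e marks the annual safety report as not applicable. The secondary hypothesis in section 2 also expects ADE not to impair workability. The reader of the final report therefore depends on this one row of Table 4 to learn how often the device caused trouble.

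**Working it through.** The plan states no ADE rate and no ADE sample size, so there is no figure of its own to reproduce. The check applies the section 8 rule to per-patient counts. The per-patient unit is an assumption.

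**Inputs**
- n = 250 patients per phase, 500 in total (section 4.d). Devices are also applied for training in phase 1 (section 7.c), so the plan does not settle whether the denominator is about 250 or about 500.
- Significance level 0.05 (section 8), taken here for the Shapiro-Wilk test.
- k = number of patients with an event, varied because the documents give no rate.

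**Step 1: which summary the rule selects.** With k patients scoring 1 and 250 - k scoring 0, Shapiro-Wilk gives p of about 1e-33 at k = 1 and about 4e-25 at k = 63. Normality is rejected throughout, so the rule selects median (IQR). At k = 0 the test cannot be computed, but the median and quartiles are again 0.

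**Step 2: when the third quartile is still zero.** Under the (n+1)p definition the position is 251 × 0.75 = 188.25, so

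Q3 = x(188) + 0.25 × [x(189) - x(188)].

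Q3 is 0 only if the 189th ordered value is 0, that is 250 - k ≥ 189, or k ≤ 61.
- k = 61 (61/250 = 24.4%): median 0, IQR 0-0.
- k = 62 (24.8%): x(189) = 1, so Q3 = 0.25.
- k = 63 (25.2%): x(188) = 1, so Q3 = 1.

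Six standard percentile definitions were compared, and the limit is 61 or 62. For n = 500 the (n+1)p position is 501 × 0.75 = 375.75, which requires 500 - k ≥ 376, or k ≤ 124. Across the six definitions the limit is 124 or 125 (24.8-25.0%).

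**Step 3: several events per patient.** In a simulated example with 1 to 3 events in each of 61 affected patients, 134 events in total are still summarised as 0 (0-0).

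**Step 4: what a proportion would show.** The exact (Clopper-Pearson) limits are the 2.5% point of Beta(k, n-k+1) and the 97.5% point of Beta(k+1, n-k). For k = 0 the upper limit is 1 - 0.025^(1/250) = 1.5%.

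| Patients with an event, of 250 | Median (IQR) | Percentage (exact 95% CI) |
|---|---|---|
| 0 | 0 (0-0) | 0% (upper limit 1.5%) |
| 1 | 0 (0-0) | 0.4% (0.0-2.2) |
| 10 | 0 (0-0) | 4.0% (1.9-7.2) |
| 25 | 0 (0-0) | 10.0% (6.6-14.4) |
| 61 | 0 (0-0) | 24.4% (19.2-30.2) |

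The middle column is the same in every row. For 0 of 500 the upper limit is 0.7%.

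**The case against.** The strongest reply is that the plan never says ADE is summarised per patient. A number of events taken once at month 6 may simply be a ward total, for which descriptive statistics means one count and no median arises. The section 8 paragraph also opens at the level of nurses and physicians, so its normality rule may not have been written with patient data in mind. Both points stand, and they make the zero summary conditional. They do not remove the gap. A normality check needs a distribution over units, the plan offers no other rule for patient-level data, and a total without a denominator cannot be read as a risk.

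A reader might infer more than the documents support:
- *That the plan asks for no confidence interval.* Section 8 has a general statement that analyses use a 95% confidence interval. It is not tied to an ADE proportion or rate, but it is there.
- *That all device problems would be hidden.* The yes/no eCRF items on removal, replacement and particularities are categorical and would be reported as numbers and percentages.
- *That SNR has the same fault.* A ratio may properly be called continuous, and the zero-median result is not shown for it. What is missing for SNR is the unit and the handling of zero counts.
- *That the hypothesis on device performance could not fail.* No decision rule in the plan rests on a median of ADE.
- *That events would read as zero at any plausible rate.* The effect stops at about 24%. The protocol's own expectation of infrequent events lies well inside that range, but the limit should be stated.

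**Conclusion.** ADE is wrongly classified. It is a count or yes/no outcome labelled continuous, with no unit and no denominator. If it is summarised per patient, the stated rule gives median 0 (IQR 0-0) for any frequency up to about 24% (61 of 250; 61 or 62 depending on the quartile definition). That range includes the low frequencies the protocol anticipates.

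The size rests on two assumptions: a per-patient unit and about 250 device wearers. With 500 wearers the limit is much the same as a percentage. That the report will in fact read 0 (0-0) is not established, because the unit is unstated.

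The change should be made, but its reach is limited to secondary, descriptive safety reporting. Neither the usability score nor the spot-check reduction is touched.

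**What to change.** In Table 4, change the ADE variable type to count/binary and replace the generic descriptive entry with:
- the total number of events, by type;
- the number and percentage of patients with at least one event among those who wore a device, with an exact 95% CI, stating whether phase 1 training devices count in the denominator;
- events per device-time, where wearing time is available. The eCRF item for minutes monitored may serve if it is confirmed to represent wearing time.

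Add an ADE item to the eCRF (yes/no, count, type), since none exists.

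As a secondary clarification, state that SNR is calculated from pooled counts of correct and false alarms, and show those counts with the monitored time. This needs the alarm counts to be captured, which the eCRF does not now do.

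The cost is an edit to the Appropriateness row of Table 4 and a few data items with definitions. If agreed before analysis, it leaves the primary endpoints unchanged.
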